6.4 Populations for Analyses

The primary analysis dataset for study outcomes will be the intent-to-treat (ITT) population wherein data from all randomized lesions will be analyzed based on the intended randomization assignment. The intent of this protocol is to apply up to 2 sessions of each treatment, but no lesions will be excluded from the ITT population based on the number of treatments actually received. The primary efficacy analysis will be performed using the ITT population. A modified intent-to-treat population will include all lesions that received at least one treatment, and the primary efficacy analysis will also be calculated for this population for comparison. The modified ITT population will be the analysis population for the primary safety endpoints.

Study outcomes will also be analyzed using a per-protocol (PP) population. The PP population includes all subjects who had no pre-specified inclusion and exclusion violations, received both CellFX and Electrodesiccation, and repeated the treatments per protocol for any lesions that were not clear at the 30-day visit.

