3.3 Randomization

All enrolled subjects will be randomized to receive the two treatments in a split-face design with CellFX being used on only one side of the face and Electrodesiccation on the other side. Randomization will be implemented through the Electronic Data Capture (EDC) system. The randomization assignment will include the type of treatment and which side of the face to treat first. For example: 1) First Treatment = CellFX and 2) Side of Face = Right. All randomized subjects will be included in the intent-to-treat analysis.

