4.0 STUDY PROCEDURES

4.1 Screening

Recruitment will be conducted via direct communication by the investigator and/or his/her designated staff, advertisement and/or office ads. The Informed Consent discussion and signature process will be conducted by the investigator and/or designated staff. No study-specific assessments will be performed prior to obtaining consent.

A Screen Failure will be defined as a subject who did not meet one or more of the following criteria:

- Did not meet all of the inclusion and/or exclusion criteria
- Did not sign informed consent
- Did not receive a randomization assignment
- Did not undergo at least one procedure (e.g. CellFX or Electrodesiccation)

A screen failure will not be assigned a subject ID and information on this subject will not be entered in the electronic database. Information will be transcribed on the enrollment/screen failure log.

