4.5.2 Definition of Enrollment

Once the subject has been consented, randomized, and has received a CellFX and Electrodesiccation treatment, the subject will be considered enrolled and each enrolled subject will be assigned a unique Study Identification Number.

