10.11 Case Report Forms /Transmission of Data

All required data for this study will be collected via web-based electronic data capture (EDC) system and entered in electronic Case Report Forms (eCRFs). A unique study identifier will be assigned to each study subject. The database will contain only the study identifier to identify the subject.

Required data will be recorded on the appropriate electronic Case Report Forms at the time of or as soon as possible after the subject visit. This will enable timely monitoring visits.

Any data discrepancies identified during data review or a monitoring visit will be queried by Pulse Biosciences and must be resolved by the site staff and Investigator in a timely manner.

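### ITT takes every randomised subject, but sections 4.1 and 4.5.2 withhold an ID, and for untreated subjects any database record, unless treatment is given

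*Combined protocol and SAP*

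**What the plan says.** On ITT, section 6.4 (Populations for Analyses) states that "data from all randomized lesions will be analyzed based on the intended randomization assignment" and makes this the primary efficacy population. Section 3.3 repeats the rule by subject: "All randomized subjects will be included in the intent-to-treat analysis". Section 6.4 also sets up the population for the primary safety endpoints: "A modified intent-to-treat population will include all lesions that received at least one treatment".

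Section 4.1 (Screening) lists the grounds for screen failure. Having no randomisation assignment is one; a separate one is "Did not undergo at least one procedure (e.g. CellFX or Electrodesiccation". The consequence is that "A screen failure will not be assigned a subject ID and information on this subject will not be entered in the electronic database". Details go on a paper trail only, the enrollment/screen failure log.

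Section 4.5.2 defines enrolment: "Once the subject has been consented, randomized, and has received a CellFX and Electrodesiccation treatment, the subject will be considered enrolled". It attaches the study ID to that status. Section 10.11 says "A unique study identifier will be assigned to each study subject" and that the database identifies subjects by this code alone.

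On the per-protocol (PP) set, section 6.4 requires, among other things, that subjects "repeated the treatments per protocol for any lesions that were not clear at the 30-day visit". Sections 3.2 and 4.7, and the footnote to Table 1, base retreatment on a GAIS rating of 1-4 at the 30-day visit. Section 3.2 makes a missed retreatment a protocol deviation.

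**The concern.** An ITT set is only as complete as the database it is drawn from. If a rule at the screening stage reaches past randomisation and prevents a record from being made, the analysis set becomes randomised and treated, whatever section 6.4 calls it. That is an exclusion decided after allocation is known.

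Three things are at stake. The ITT denominator would be wrong. The lesions concerned would not appear as missing in the longitudinal and tipping-point analyses of section 6.6. And a subject treated on one side only could have outcome and safety observations with no identifier to file them under.

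The PP wording is a lesser matter. PP does not decide study success under section 6.1.3, but it is a planned supporting analysis in a non-inferiority trial, so its membership should follow the same rule that defines a missed retreatment.

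**Working it through.** No arithmetic decides this point. The passages are set side by side for each kind of randomised subject.

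| Randomised subject | Sections 3.3 and 6.4 | Section 4.1 | Section 4.5.2 |
|---|---|---|---|
| No procedure on either side | All lesions in ITT, none in mITT | Screen failure: no ID, no database record | Not enrolled, no ID |
| Treated on one side only | All randomised lesions in ITT, treated ones in mITT, subject not in PP | Not a screen failure, since one procedure is enough | Not enrolled, no ID |
| Treated on both sides | ITT and mITT | Not a screen failure | Enrolled, ID assigned |

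Only the third row is consistent throughout. In the first row, sections 4.1 and 3.3 cannot both be followed. In the second, section 6.4 has a place for the lesions but section 4.5.2 gives the subject no ID. Section 10.11 does not settle it, because the document does not say whether such a person is a study subject.

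**Can the first two rows occur?** Yes, but rarely. Table 2 puts randomisation and both first treatments at Visit 1. In section 4.5.3 the assignment is followed by lesion sizing and labelling, the blinded baseline assessment, photographs and local anaesthesia, and only then by treatment. There is an interval in which a subject can stop, but it is short.

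**Would the primary estimate change?** Both 60-day co-primary endpoints, and the 30-day texture endpoint, are timed from the last treatment. A subject with no treatment has no such outcome, so the primary GEE model has nothing from that subject with or without the record. A subject treated on one side can have outcomes on the treated lesions, and those could be lost.

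**Does the sample-size target give a size?** The plan's own figures in section 6.3 are coherent: 260 / 52 = 5 lesions per subject, and 52 / (1 - 0.10) = 57.8, rounded up to 58, consistent with up to 60 enrolled. But the 260 are lesions with follow-up at 60 days after the last treatment, and the 60 are enrolled subjects, which under section 4.5.2 means treated with both. An untreated subject is in neither count, so no percentage of 260 applies.

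**PP wording.** Section 4.7 has two scales rated at 30 days: GAIS and the 4-point clearance scale. Section 6.7.1 uses Not Clear as the label for score 3 on the latter. The PP sentence in section 6.4 names neither scale. If its reference to the protocol brings in the GAIS 1-4 trigger, the two rules agree. If the clearance scale is meant, a subject could breach one rule and satisfy the other. The documents give no joint distribution of the two ratings, so the number of subjects affected cannot be estimated.

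**The case against.** The best case for the plan runs as follows. The randomisation is issued through the EDC system (section 3.3) and a screen failure is written on a log (section 4.1), so an untreated subject can be traced. Section 6.4 already settles the analysis sets for a subject treated on one side. In the PP sentence, the reference to repeating treatment as the protocol requires most naturally means the only retreatment rule there is, GAIS 1-4. Section 6.0 defers further detail to a SAP, which could settle the definitions.

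Much of this stands. Traceability limits the harm, and the PP part is a request for clearer wording, not a contradiction. It does not remove the ITT conflict: a log line and an allocation are not an analysable record, and section 4.1 expressly bars the record. No SAP text available for this review resolves it.

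Four stronger readings are tempting and should not be drawn:

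- A reader might divide the 4 to 10 lesions a subject may contribute by 260 and call that the loss. The 260 counts lesions with 60-day follow-up, so the denominator is wrong.
- A reader might infer from the separate mITT definition that ITT was meant to hold wholly untreated subjects. Both sets are defined by lesion, and they can differ through one untreated lesion in a treated subject.
- A reader might count the combinations of clearance score and GAIS rating on which the two rules differ and treat that as the size of the PP problem. Combinations are not lesions, and some are implausible.
- A reader might take the mapping in section 6.3 to show that the plan expects lesions rated Clear with GAIS 1-4. That mapping is an assumption for a power simulation on earlier-study data. It does not describe live ratings at day 30.

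**Conclusion.** The ITT conflict is real and in the current text. Followed as written, sections 4.1 and 4.5.2 exclude randomised subjects whom sections 3.3 and 6.4 include. They also leave a subject treated on one side without an ID, with a possible loss of outcome and safety data.

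Severity is minor. Few or no subjects are likely to be affected, on the assumption that treatment follows randomisation within Visit 1 as Table 2 shows. For wholly untreated subjects the harm is to the ITT count and the missing-data account, not to the primary estimate. For a subject treated on one side the harm depends on whether sites follow section 4.5.2 literally, which the documents cannot tell us.

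The PP wording is a secondary clarification of unknown and possibly zero effect.

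**What to change.** In section 4.1, end screen failure at randomisation by removing the criterion about not having had a procedure for anyone already randomised. In section 4.5.2, assign the study ID at randomisation. State in both that every randomised subject stays in the database and in the ITT set, with the reason for any treatment not given.

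In section 6.4, reconcile the PP retreatment condition with sections 3.2 and 4.7, so that PP membership names the same scale and cut-off as the retreatment rule. This review takes no view on what the retreatment rule should be.

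The cost is wording in three sections and at most a few extra database records.

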6.5 Sub-Group Analyses

Primary and secondary endpoints will be evaluated for the ITT and PP populations, as well as analyzed in strata based on the following sub-groups:

- Age
- Prior treatment for treated SH lesions
- Gender
- Fitzpatrick score (I/II vs III)
- Clinical Site
- Treatment Energy Level
- Size of CellFX Treatment Tip
- Total Energy Density
- Secondary Treatments

These analyses are meant to assess consistency of treatment effects only, and this study is not powered for inference within subgroups.

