3.2 Study Design

This study is designed as a multicenter, single-blinded, prospective, randomized, comparison IDE study between CellFX System and Electrodesiccation.

The Principal Investigator will select a sub investigator to be the blinded investigator to classify the healing characteristics and aesthetic appearance of each subject's selected lesions at baseline and treated lesions post treatment and at 7-days, 30-days, and 60-days following the last CellFX

treatment or Electrodesiccation. This sub investigator will be blinded to the treatment assignment. The subject may not be blinded to the treatment assignment.

Eligible subjects with a minimum of 4 and up to 10 SH lesions meeting the inclusion and exclusion criteria will be enrolled. The SH lesions may be present anywhere on the face except the scalp, nose and within the orbital region of the face. The subject must have at least two SH lesions on each side of the face. Subjects will be randomized to receiving the two treatments in a split-face design with CellFX being used on only one side of the face and Electrodesiccation on the other side. A minimum of two lesions must be treated with CellFX and a minimum of two lesions must be treated with Electrodesiccation per subject. Selected lesions for each treatment modality must be clearly separated in distance from each other so that lesion treatment and side effects can be assessed by the blinded site investigator.

All selected and qualifying study lesions will receive at least one CellFX or Electrodesiccation treatment. Each subject will be evaluated by the blinded site investigator at 7-days, 30-days, and 60-days post-initial CellFX and Electrodesiccation treatments. At the 30-day follow-up visit, if any lesion is rated 1-4 on the Global Aesthetic Improvement Scale (GAIS), the lesion must receive an additional treatment. In case of a second treatment, the subject will be evaluated by the blinded site investigator at 30-days and 60-days post-retreatment. Photography of the study lesions will be captured along with the blinded site investigator assessments at all visits.

Note:

Eligible lesions that should be treated and do not receive a retreatment will be considered a protocol deviation. The reason(s) for not receiving an additional treatment will be collected on the electronic case report form (eCRF). These subjects will remain in the study and will be included in the ITT population.

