3.4 CellFX Procedure

The intended CellFX treatment device is described as the CellFX® System using the skin contacting component referred to as the “tip” ranging in sizes from 1.5 mm x 1.5 mm to 5.0 mm x 5.0 mm in length and width and 2.0 mm in depth. Each tip will be used with pre-determined energy settings displayed on the CellFX Console and are provided in **Table 1**. These energy settings do not exceed the maximum safe ranges of settings previously tested in clinical studies. A local anesthetic will be used to manage potential treatment discomfort during the CellFX treatment. All subjects will be monitored for muscle “twitching” on the face during each CellFX treatment and the subjects will be asked whether they felt any muscle “twitch” during the treatment.

Table 1: Energy Settings per Tip Size and Fitzpatrick Skin Type

Tip Size (L x W, mm)	Fitzpatrick Skin Type	1 st Treatment Level mJ/mm ³	Re-Treatment Level mJ/mm ³ *
1.5 x 1.5	I-II	190	150
1.5 x 1.5	III	150	150
2.5 x 2.5	I-II	60	30
2.5 x 2.5	III	30	30
5.0 x 5.0	I-II	45	30
5.0 x 5.0	III	30	30

**If a lesion was rated as 1-4 on the GAIS scale at the 30-day follow-up visit due to a mistargeted lesion that was confirmed by a photograph taken immediately post CellFX procedure, it is recommended to use the first treatment level energy settings.*

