4.5.3 CellFX Treatment / Electrodesiccation Treatment

- Up to 10 clinically diagnosed SH lesions that meet the study criteria will be selected by the treating investigator and prior to assigning lesions the subjects should have baseline photos taken.
- The site will log onto the Captivate EDC system. The randomization assignment will include the type of treatment and which side of the face for CellFX and Electrodesiccation.
- A template may be used to determine which treatment tip size will be used for each lesion – sizes range between 1.5 mm x 1.5 mm and 5.0 mm x 5.0 mm. The identified lesions will be numerically labeled.
- The blinded site investigator will then perform a baseline lesion(s) assessment.
- Photographic images of each selected lesion will be taken prior to using local anesthesia/numbing.
- Local anesthesia/numbing will be applied to all selected study lesions.
- Each lesion randomized to CellFX will be treated with pre-determined energy settings; each lesion randomized to Electrodesiccation will be treated as defined in **Section 3.5**.
- The subject will be asked to rate his/her pain immediately after each lesion treated with the CellFX and Electrodesiccation procedures by using a numerical rating score.
- The subjects will be asked whether they felt muscle twitching immediately after each lesion treated with CellFX.
- Post procedure lesion assessment will be performed by the blinded site investigator.
- Photographic images of each selected lesion will also be taken post-treatment.
- A light bandage and/or any physician recommended dressing may be applied before the subject leaves the clinic.
- Any adverse events will be identified and documented.

4.6. 7-Day Follow-up Visit

- Photographic images of each of the study lesions will be taken with pre and post lesion markings.
- All lesions will be clinically assessed by the blinded site investigator.
- Any adverse events will be identified and documented.

4.7 30-Day Follow-up Visit (Optional CellFX/Electrodesiccation Treatment #2)

- Photographic images of each of the study lesions will be taken with pre- and postlesion markings.
- All lesions will be clinically assessed by the blinded site investigator and rated using GAIS scale and the 4-point lesion clearance scale.
- If any lesion is rated 1-4 on the GAIS scale, a second treatment with CellFX or electrodesiccation will be performed to the previously treated lesion.

In case of a second CellFX or Electrodesiccation treatment:

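### Four of the nine Section 6.5 subgroup factors do not suit a check of consistency between devices: three are specified only for CellFX lesions, and one follows from the lesion's own Day-30 rating

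*Combined protocol and SAP*

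**What the plan says.** Section 6.5 evaluates the primary and secondary endpoints in the ITT and PP populations, "as well as analyzed in strata based on the following sub-groups". Nine factors follow: age, prior treatment of the lesions, gender, Fitzpatrick type, clinical site, treatment energy level, "Size of CellFX Treatment Tip", "Total Energy Density" and secondary treatments. The purpose and its limit are given in one sentence: "These analyses are meant to assess consistency of treatment effects only, and this study is not powered for inference within subgroups".

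Four other places matter.

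- **Section 3.4** ties energy to the CellFX tip: "Each tip will be used with pre-determined energy settings displayed on the CellFX Console and are provided in" Table 1, by tip size and Fitzpatrick type.
- **Section 3.5**, on electrodesiccation, names a needle and an anesthetic but no tip size, energy level or energy density.
- **Section 3.2** sets the retreatment rule at the 30-day visit: "if any lesion is rated 1-4 on the Global Aesthetic Improvement Scale (GAIS), the lesion must receive an additional treatment". Section 4.7 repeats it.
- **Section 4.5.3** has an optional sizing step, listed after the randomization step: "A template may be used to determine which treatment tip size will be used for each lesion". It does not say that a size is recorded for electrodesiccation lesions.

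**The concern.** The effect that the trial estimates is the CellFX proportion minus the electrodesiccation proportion, per lesion (Sections 6.1.1 and 6.1.2). To ask whether it is consistent across a factor, each level must contain lesions from both devices, and the grouping must not itself be a result of treatment. Four of the nine factors fail one or both conditions.

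At stake is the reading of the subgroup tables. For the device factors, a reader would look for a between-device contrast that the data cannot supply. For secondary treatments, a contrast can be computed but compares lesions selected by early response. If the devices differ in how often they need a second session, the strata can suggest a device difference where there is none, or distort a real one.

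**Working it through.** The plan gives no figure for the subgroups, so there is none to reproduce. The check sorts the nine factors, shows what is estimable, and then sizes the selection effect.

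**1. Sorting the factors**

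| Factor | Specified for electrodesiccation lesions? | Fixed before treatment response? |
|---|---|---|
| Age, gender, Fitzpatrick type, site, prior treatment | Yes | Yes |
| Treatment energy level | No (Table 1 is CellFX only) | First level yes; see below |
| CellFX tip size | No | Yes |
| Total energy density | No; not defined anywhere | No, if summed over sessions |
| Secondary treatments | Yes | No (Day-30 GAIS) |

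Five factors suit the purpose and four do not. In Table 1 the first and re-treatment levels differ for every tip in Fitzpatrick I-II (190/150, 60/30, 45/30) and are equal in type III. Energy level is therefore ambiguous for a retreated type I-II lesion. The first-treatment level is fully determined by tip size and Fitzpatrick group, so it adds little to those two factors.

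**2. CellFX-only strata**

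The evaluable target is 260 lesions (Section 6.3), about 260/2 = 130 per device. Within any tip-size level the number of electrodesiccation lesions is 0. The model there is response = a + b × device with device = 1 for every lesion, so the two design columns are identical. The rank is 1 of 2, and b cannot be estimated.

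**3. The retreatment stratum**

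Inputs from the documents: 73% response (Section 6.3), and retreatment rates of 12% and 27%, taken from the SH-009 summary in Section 1.5. Both rates are CellFX rates at different energy settings. The documents give no electrodesiccation retreatment rate, so the gap between devices is an assumption. So is the correlation ρ between Day-30 and final status.

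Model, with no device difference in final outcome: X (Day-30 difficulty) and Y (final difficulty, after all treatment) are standard normal with correlation ρ. A lesion is retreated if X > c, where c = z(1 − r) and r is the device's retreatment rate. It responds if Y < d, where d = z(0.73) = 0.613. With Φ₂ the bivariate normal distribution function:

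- response if not retreated = Φ₂(c, d; ρ) / (1 − r)
- response if retreated = [0.73 − Φ₂(c, d; ρ)] / r

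| ρ | Retreated: r = 12% | Retreated: r = 27% | Difference | Not retreated: r = 12% | Not retreated: r = 27% | Difference |
|---|---|---|---|---|---|---|
| 0.3 | 54.7% | 60.1% | −5.4 | 75.5% | 77.8% | −2.3 |
| 0.5 | 40.3% | 50.2% | −9.9 | 77.5% | 81.4% | −4.0 |
| 0.7 | 23.8% | 38.5% | −14.7 | 79.7% | 85.8% | −6.1 |

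Differences are in points, lower-rate device minus higher-rate device, taken before rounding. Check at ρ = 0.5: 0.12 × 40.3 + 0.88 × 77.5 = 73.0 and 0.27 × 50.2 + 0.73 × 81.4 = 73.0. Both devices have the same overall response, yet the one retreated less looks worse in both strata. Its retreated group holds only the hardest lesions, and its other group keeps some hard lesions that the other device would have moved out.

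Swapping the rates reverses the signs. Equal rates give 0. At 14% versus 12% the largest difference over the same range of ρ is 2.4 points.

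**4. Precision of that stratum**

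At 12% to 27% retreatment, 130 × 0.12 = 15.6 to 130 × 0.27 = 35.1 lesions per device are retreated. With k per device, independence and 73% response, the 95% half-width is 1.96 × √(2 × 0.73 × 0.27 / k), which is 31 points at k = 15.6 and 21 points at k = 35.1.

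**The case against.** **The subgroups are descriptive and unpowered.** This is true and limits the importance of the point. Section 6.1.3 rests success on the co-primary tests plus a CellFX response estimate above 60%, and no subgroup result enters. The half-widths above also show that the retreated stratum would be noisy. But low power concerns precision. It does not supply a missing comparator or remove selection.

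**The tables can still be made.** This also stands in part. A reader might infer that strata by tip, energy and density cannot be formed at all. The documents do not support that: tables of CellFX lesions alone are feasible, and Section 1.5 reports SH-009 by energy setting. Section 3.1 lists response against each lesion's own pre-treatment appearance among the objectives, so a within-CellFX reading is possible. Because the design is split-face, a subject-level stratum would also have a comparator where all of a subject's CellFX lesions share a setting. Section 6.5 specifies neither reading, and tip size is chosen lesion by lesion.

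**The sizing template covers each lesion.** It is optional, comes after randomization in the list, and carries no stated recording for the electrodesiccation side. It shows that a repair is feasible, not that one is planned.

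**A SAP may deal with it.** Section 6.0 defers detail to the SAP, but the documents contain no further subgroup rule. The point is therefore about Section 6.5 as written.

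**The bias is hypothetical.** A reader might infer that the retreatment strata will be biased in a known direction, or that any contrast between them would come wholly from selection. Neither is supported. With equal rates there is no bias, and the sign depends on which device is retreated more. If a real device effect exists, risk differences can also vary between strata simply because base rates differ. The zero-difference case above was chosen to keep that scale effect out.

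**Conclusion.** The point holds in a limited form. Four of the nine factors do not serve the purpose that Section 6.5 states. For energy level, tip size and total energy density this follows from the text alone and needs no assumption: at lesion level no between-device difference is estimable. For secondary treatments the defect is conditional on unequal retreatment rates. Over the assumed range it amounts to about 5 to 15 points among retreated lesions and 2 to 6 points among the others; it is small when the rates are close and zero when they are equal. Those sizes rest on the assumed rates, the bivariate normal model and ρ from 0.3 to 0.7, and should be read as illustration, not prediction.

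A reader might infer that the trial's conclusion is at risk. It is not: the co-primary estimates, the error rate and the success criteria are untouched. The point is worth acting on because the change is nearly free and keeps a misleading table out of the report.

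**What to change.** 1. Remove secondary treatments from the strata in Section 6.5. Report the retreatment rate as an outcome by device, with a difference and confidence interval that account for within-subject correlation.
2. Label tip size, energy level and total energy density as descriptive tables of CellFX lesions only. Define total energy density, and say whether it sums over sessions and which session's level classifies a retreated lesion.
3. Only if a size-related consistency check is wanted: record a baseline lesion-size class for every lesion on both sides before the side assignment is opened, and stratify on that. Together with Fitzpatrick I-II versus III it determines the first-treatment level in Table 1, so the question behind tip and energy gains a comparator.

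Items 1 and 2 cost wording in the protocol or SAP, with no new data. Item 3 costs a small protocol and eCRF change, since the sizing step in Section 4.5.3 is optional and listed after randomization. It has to be in place before enrollment, because the size class must be recorded prospectively. No visits are added and no treatment rule changes.
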